Neuromuscular mechanisms will be quantified before and immediately after a 2-week intervention. Mechanisms will include a comprehensive group of peripheral (ankle joint position sense, plantar light-touch discrimination thresholds), spinal (H-reflex of the soleus and fibularis longus), and supraspinal measures (cortical activity during stance using electroencephalography [EEG], corticomotor excitability and mapping of the soleus and fibularis longus via transcranial magnetic stimulation [TMS], and sensory organization strategies during stance). Our primary mechanism of interest is sensory organization strategies. Sixty CAI patients will be randomized into three equal groups (ankle joint mobilization, plantar massage, control) to complete 6 treatment sessions over 2-weeks.

Hypothesis 1. Both interventions, relative to the control group, will result in significant sensory organization strategy changes, representing a reduction in the CAI patient's reliance on visual information during stance.

Hypothesis 2. Each intervention will result in unique combinations of peripheral, spinal, and supraspinal mechanistic pathways relative to the control group.

Aim 2: Determine the associations among peripheral, spinal, and supraspinal neuromuscular mechanisms, secondary biomechanical measures, and sensory organization strategies in CAI patients. These associations will be quantified to elucidate the unique combination of peripheral, spinal, and supraspinal mechanistic pathways thought to contribute to a reducing in the reliance of visual information during stance. Secondary measures which will include jump landing and gait biomechanics will be assessed before and immediately after the 2-week interventions. We will use an analytical approach (see statistical analysis) to determine simple associations at baseline, post-test, and among change scores in neuromuscular mechanisms and secondary measures.

Hypothesis 1. Each intervention will result in unique combinations of changes in peripheral, spinal, and supraspinal mechanistic pathways will be strongly associated with changes sensory organization strategies.

Hypothesis 2. Each intervention will result in secondary measure changes associating with changes in sensory organization strategies as well as peripheral, spinal, and supraspinal mechanistic pathways.

3 Study Design

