To achieve Aim 1, 18 participants per group are needed to ensure significant changes in the primary mechanism of interest following both interventions relative to the control group. Between group (i.e. massage vs. control [$d=0.53$] & mobilization vs. control [$d=0.69$]) pre to post effect sizes from our preliminary data (See Preliminary Studies) were used to calculate the needed sample size. Using GPower (3.1), a repeated measures, between factors ANOVA model for three groups and two time points was used. Parameters included a purposefully conservative intra-measure correlation= 0.90 , $\alpha=0.05$, and $1-\beta=0.90$. To achieve Aim 2, 16 participants per group are needed to identify significant correlations. This value was calculated based on previously established correlations between neuromuscular mechanisms and biomechanical measures of postural control.^{16, 95} Parameters for this analysis included a correlation of $r=0.5$ (range from literature: 0.50 to 0.58), an $\alpha=0.05$, and $1-\beta=0.90$. Thus, we will recruit 20 participants per group and plan for a 10% dropout rate, which would leave 18 subjects per group. Our previous work⁴² had a 98.75% (79/80) retention rate using the same intervention protocol and all participants completed 100% of the treatment sessions.

7 Inclusion & Exclusion Criteria

Inclusion criteria will consist of the following:

- Male or female 18-45 years of age
- History of ankle sprain with at least two episodes of “giving way” within the past six months
- Score of ≥ 5 on the Ankle Instability Instrument (All)
- Score of $\leq 90\%$ on the FAAM-ADL
- Score of $\leq 80\%$ on the FAAM-S.

Exclusion criteria will consist of the following:

- Younger than 18 or older than 45 years
- No history of ankle sprain or episodes of “giving way” in the past six months
- Score of ≤ 5 on the Ankle Instability Instrument (All)

- Score of $\geq 90\%$ on the FAAM-ADL
- Score of $\geq 80\%$ on the FAAM-S.
- An acute ankle sprain within the past 6 weeks.
- Previous history of lower extremity surgery with internal derangements, reconstructions, or repair
- Lower extremity injury within the past 6 months (other than ankle sprains)
- Presence of balance deficits or conditions known to affect balance as noted on the Balance Questionnaire including diabetes and/or vertigo.

8 Randomization Plan

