To achieve Aim 2 and determine the associations among sensory organization strategies, neuromuscular mechanisms, and secondary measures following ankle joint mobilization and plantar massage interventions, we will calculate associations at baseline, at the post-test, and among change scores. These associations will be calculated using Pearson Correlation Coefficients that will be interpreted as: ≤ 0.29 as negligible, 0.30-0.49 as low, 0.50-0.69 as moderate, 0.70-0.89 as high, and ≥ 0.9 as a very high correlation.¹³⁵ The models will then be adjusted for identified covariates using a general linear model and an exploratory alpha level of 0.10. We anticipate associations that will provide insights about how to specifically leverage the manual therapies mechanisms to target specific neuromuscular impairments and biomechanical deficits associated with CAI.

All experimental conditions are detailed to ensure reproducibility and the proposed analytic plan ensures unbiased treatment and interpretation of the data. We are committed to full transparency in reporting the results and to making the data available upon request for unbiased review.

To explore how individual response variability influences plausible neuromuscular mechanisms, we will use a Bayesian statistical approach.^{71, 94, 144, 145} More specifically, we will determine how patient characteristics (e.g. age, height) and baseline measures influence the probability of having a meaningful change in % Modulation and other neuromuscular mechanisms. Predicting treatment response with only demographic and baseline data would suggest that the neuromuscular mechanism(s) of ankle joint mobilization and plantar massage may be modulated by the patient's sensorimotor constraints.

13 Data Management

Data will be collected both in hard copy & electronically. All computers in the research laboratories are password protected. As soon as feasible, the PIs will transfer the, already de-identified, electronic data to Sharepoint. In order to protect the integrity of the original data files, copies will be made to be used for data manipulation. Any data file that is amended, cleaned, or updated will be given a new name with the corresponding name of the original file followed by `_modified` and dated with the `month_`, `day_`, and 2-digit year it was modified (i.e. `IC01_trial_1_modified_10_11_18`).

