To achieve Aim 1 and quantify changes caused by the ankle joint mobilization and plantar massage interventions, neuromuscular mechanisms will be submitted to separate 2-way repeated measures (Group x Time) ANOVAs. MANOVAs may be used based on inter-item correlation coefficients found during the preliminary analysis of the data. Pairwise comparisons, when appropriate, will determine the location of significant interactions. An alpha level of 0.05 will be used to assess changes in the primary mechanism of interest (% modulation). An exploratory alpha level (0.10) will be used on all other peripheral, spinal, and supraspinal mechanisms and secondary measures to reduce the chance that possible changes would be overlooked in this initial R21 investigation. Hedge's G effect sizes and confidence intervals based on the pre-to-post change scores⁴² will also be calculated and interpreted as follows: less than 0 as small, 0.31-0.7 as moderate, and greater than 0.71 as large. Finally, control group data will be used to calculate the minimal detectable change (MDC) scores for all mechanisms and secondary measures;^{42, 98, 134} The MDC allows us to evaluate the interventions effects relative to the stability of the measures over time. This 3-pronged approach affords us multiple criteria on which to base the interpretation of our results and power future clinical trials.

To achieve Aim 2 and determine the associations among sensory organization strategies, neuromuscular mechanisms, and secondary measures following ankle joint mobilization and plantar massage interventions, we will calculate associations at baseline, at the post-test, and among change scores. These associations will be calculated using Pearson Correlation Coefficients that will be interpreted as: <0.29 as negligible, 0.30-0.49 as low, 0.50-0.69 as moderate, 0.70-0.89 as high, and >0.9 as a very high correlation.¹³⁵ The models will then be adjusted for identified covariates using a general linear model and an exploratory alpha level of 0.10. We anticipate associations that will provide insights about how to specifically leverage the manual therapies mechanisms to target specific neuromuscular impairments and biomechanical deficits associated with CAI.

A.8.2. If this is a pilot study, please describe the future study and say how its study design, aims, sample size, and methods differ from the pilot study you are proposing.

NA

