A.8.3. Provide a compelling justification for the proposed sample size in terms of the likelihood of achieving each aim.

Changes in sensory organization strategies has been chosen as the primary mechanism of interest and will be assessed by calculating the % Modulation of the resultant center of pressure velocity between eyes open and eyes closed stance.³³

To achieve Aim 1, 18 participants per group are needed to ensure significant changes in the primary mechanism of interest following both interventions relative to the control group. Between group (i.e. massage vs. control [d=0.53] & mobilization vs. control [d=0.69]) pre to post effect sizes from our preliminary data (See Preliminary Studies) were used to calculate the needed sample size. Using GPower (3.1), a repeated measures, between factors ANOVA model for three groups and two time points was used. Parameters included a purposefully conservative intra-measure correlation=0.90, $\alpha=0.05$, and $1-\beta=0.90$. To achieve Aim 2, 16 participants per group are needed to identify significant correlations. This value was calculated based on previously established correlations between neuromuscular mechanisms and biomechanical measures of postural control.^{16, 95} Parameters for this analysis included a correlation of r=0.5 (range from literature: 0.50 to 0.58), an $\alpha=0.05$, and $1-\beta=0.90$. Thus, we will recruit 20 participants per group and plan for a 10% dropout rate, which would leave 18 subjects per group. Our previous work⁴² had a 98.75% (79/80) retention rate using the same intervention protocol and all participants completed 100% of the treatment sessions.

A.8.4. Summarize the plans for data management.

- Data entry will be confirmed by at least two members of the research team.
- The research team will use REDCap to maintain their database.
- The PI will be responsible for database management.

A.9. Identifiers

A.9.1. Check which of the following identifiers you already have or will be receiving, or select "None of the above."

- Names (this would include names/signatures on consent forms)
- Telephone numbers
- Any elements of dates (other than year) for dates directly related to an individual, including birth date, admission date, discharge date, date of death. For ages over 89: all elements of dates (including year) indicative of such age, except that such ages and elements may be aggregated into a single category of age 90 and older

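### The 90% power claimed for Aim 2 with 16 per group does not hold for a correlation within one arm: r=0.5 needs 37 (two-sided) or 31 (one-sided), and 18 per arm give 59% or 71%

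*Combined protocol and SAP*

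**What the plan says.** Section 6 of the study protocol (Appendix 1) sizes Aim 2 in one sentence: "To achieve Aim 2, 16 participants per group are needed to identify significant correlations". The inputs follow, here as worded in A.8.3 of the IRB protocol (Appendix 18): "Parameters for this analysis included a correlation of r=0.5 (range from literature: 0.50 to 0.58"), with alpha 0.05 and power 0.90. M.5 of the manual carries the same text. None of the three places gives the sidedness or names the procedure used for this calculation. Recruitment is 20 per group, and 10% dropout leaves 18, which is the Aim 1 requirement.

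The first Aim 2 hypothesis (Section 2) reads in part: "Each intervention will result in unique combinations of changes in peripheral, spinal, and supraspinal mechanistic pathways will be strongly associated" with changes in sensory organization. The second is also framed for each intervention.

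Section 12 says of the analysis: "we will calculate associations at baseline, at the post-test, and among change scores" (quoted from the matching text in A.8.1). It adds: "These associations will be calculated using Pearson Correlation Coefficients that will be interpreted as", followed by size bands in which 0.50-0.69 is moderate and 0.70-0.89 is high. Covariate-adjusted models then use a "general linear model and an exploratory alpha level of 0.10". Section 12 names the two therapies together ("following ankle joint mobilization and plantar massage interventions"). It does not say whether correlations are computed within arms or across them.

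**The concern.** Sixteen is a small number for detecting a correlation of 0.5 with 90% power. If the correlation is tested separately in each therapy arm, as the hypotheses imply, the stated inputs should give a figure about twice as large.

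What is at stake is how an Aim 2 null result is read. A reader told that each group has 90% power would take a non-significant correlation in one therapy arm as fair evidence that the pathway is absent there. If real power is nearer 60%, that inference is not available.

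**Working it through.** **Inputs.** r=0.5 (literature range 0.50 to 0.58), alpha 0.05 and power 0.90 come from Section 6. Group sizes are 16 (stated), 18 (after dropout) and 20 (recruited), in three arms. The null value is not stated and is taken as 0. Sidedness is not stated, so both are shown.

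**Method.** The test uses t = r·√(n−2)/√(1−r²) on n−2 degrees of freedom. For bivariate normal data, power is the noncentral-t tail probability with noncentrality [ρ/√(1−ρ²)]·√W, averaged over W ~ χ² on n−1 degrees of freedom. This is exact.

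**Can 16 be reproduced within one arm?** No. Required n for 90% power:

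| True r | two-sided 0.05 | one-sided 0.05 or two-sided 0.10 |
|---|---|---|
| 0.50 | 37 (90.1%; n=36 gives 89.3%) | 31 (90.6%; n=30 gives 89.7%) |
| 0.58 | 26 | 22 |

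Hand check by Fisher z, n = [(z_α + z_β)/atanh(r)]² + 3, with atanh(0.5) = 0.5493:
- Two-sided: [(1.960 + 1.282)/0.5493]² + 3 = 37.8, so 38.
- One-sided: [(1.645 + 1.282)/0.5493]² + 3 = 31.4, so 32.

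A fixed-regressor noncentral t gives 34 and 28. No method gives 16.

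**Power within one arm:**

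| n per arm | r=0.50, two-sided 0.05 | r=0.50, one-sided 0.05 or two-sided 0.10 | r=0.58, two-sided 0.05 |
|---|---|---|---|
| 16 | 53% | 66% | 69% |
| 18 | 59% | 71% | 75% |
| 20 | 64% | 76% | 80% |

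At n=18, 90% power needs |r| of about 0.67 (two-sided 0.05) or 0.62 (two-sided 0.10). Both lie above the plan's literature range. An observed r=0.5 at n=18 has a Fisher 95% interval of tanh(0.5493 ± 1.960/√15), that is 0.04 to 0.78.

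**Does simple pooling give 16?** Dividing the exact totals over arms gives 37/2 → 19 or 31/2 → 16 for two arms, and 37/3 → 13 or 31/3 → 11 for three. Only the one-sided, two-arm version reaches 16.

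**Routes that do reach 16, and what each adds or changes:**

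| Route | Result | Not in the text |
|---|---|---|
| Two active arms pooled, one-sided | 31/2 = 15.5 → 16; n=32 gives 91.4% (85.3% two-sided) | pooling, sidedness |
| Three arms pooled, two-sided alpha 0.05/3 | N=48, 90.7%; 48/3 = 16 | pooling, Bonferroni correction |
| Three arms pooled, three-predictor F test, R²=0.25 (f²=0.25/0.75, noncentrality N·f²) | N=47, 90.3%; 47/3 = 15.7 → 16 | pooling, number of predictors |
| One arm, 0.5 read as r² (r=0.707), two-sided | n=16, 90.8%; n=15, 88.6% | contradicts the stated r=0.5 |

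**Pooled power, for contrast.** If a within-arm r=0.5 is common to all arms and arm is adjusted for (effective n = n − arms + 1), two-sided power at 0.05 is 88% for two arms (n=36) and 97% for all 54 completers.

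**The case against.** The best reply is that no passage states a within-arm analysis. A per-group figure can be a total divided over equal arms. Aim 2 is set in CAI patients generally, and Section 12 names both therapies together. Baseline associations precede randomization, so splitting them by arm has little rationale. Several pooled routes arrive at 16. This stands as far as it goes: a reader might infer that the sponsor made an arithmetic slip, and the documents do not support that, because the route to 16 cannot be identified. It does not rescue the stated power. A correlation pooled across therapies cannot show what each intervention does, and that is what the hypotheses are about.

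Second, Hypothesis 1 speaks of strong association. If that means the plan's high band, 18 per arm give about 93% power at r=0.70 (two-sided 0.05). This is true, but Section 12 does not define a strong association, and the sizing rests on 0.5, which the plan's own bands call moderate.

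Third, Section 12 reads Pearson coefficients by size and sets an exploratory alpha for the adjusted models. That limits the damage. Section 6 nevertheless chose significant correlations as its criterion, at an alpha that differs from the 0.10 in Section 12, and at 0.10 power is still only 71%.

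**Conclusion.** The power statement is wrong as written for the per-intervention hypotheses. Those inputs need 37 or 31 per arm, not 16. With 18 per arm, a true r=0.5 would be missed 41% of the time at two-sided 0.05 and 29% at two-sided 0.10. This rests on bivariate normality, a null of zero, and reading the hypotheses as within-arm. Approximate methods move the required n by 1 to 3 and power by 2 to 5 points, which does not alter the conclusion.

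Three stronger readings are not supported:
- A reader might infer that the trial is too small. Enrolment is set by Aim 1, and neither it nor the primary % Modulation test depends on the 16.
- A reader might infer that every Aim 2 analysis is underpowered. An association pooled over all arms would have ample power at r=0.5.
- A reader might infer that significance in one arm only will be taken as proof of a pathway unique to that therapy. The plan contains no such rule.

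The correction should be made, but it concerns a partly exploratory aim and no primary conclusion.

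**What to change.** In Section 6, M.5 and A.8.3, state which Aim 2 correlations are within-arm and which are pooled, the sidedness, and one alpha consistent with Section 12.

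For within-arm correlations, replace the claim of 90% power from 16 per group with what 18 per arm provide at r=0.5: 59% at two-sided 0.05 and 71% at two-sided 0.10. Add that 90% power at two-sided 0.05 is reached only for |r| of about 0.67 or more. Report these correlations as exploratory estimates with confidence intervals.

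For any pooled association, give its power separately: about 97% at n=54 with arm adjustment, two-sided 0.05, if r=0.5 is common to all arms. Include an arm term for post-test and change-score associations, and do not present the result as a test of the per-intervention hypotheses.

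The cost is rewording in three places and, where associations are pooled, an arm term in a model already planned. The stated Aim 2 power becomes less favourable. No extra patients are needed.
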